# 8.3.5 Assessment of Palatability and Acceptability

Palatability and acceptability will be assessed using the Palatability Acceptance Assessment. Palatability is measured using a 5-point facial hedonic scale depicting various degrees of tolerance. Participants will also be asked to report any problems experienced while taking the medication. All participants will rate the palatability and acceptability of the PFS formulation on the first and last days of the PFS treatment phase.

The Palatability Acceptance Assessment should be implemented with the following recommendations:

- Ages 2 through 4 years: Completion by observer (parent/caregiver or health care provider).
- Ages 5 through 13 years: Combined completion: the child participant should complete the faces question and the observer should complete the remaining questions.
- Ages 14 through 17 years: Completion directly by the child participant when possible.

Observer assessments should be based on what the parent/legally acceptable representative/ caregiver/health care provider has observed directly during and after medication administration, including the participant's facial expressions, behavior, and what the participant says. Only individuals who have directly observed the participant taking the study treatment should complete the assessment.

# 8.4 Adverse Events (AEs), Serious Adverse Events (SAEs), and Other Reportable Safety Events

The definitions of an AE or SAE, as well as the method of recording, evaluating, and assessing causality of AE and SAE and the procedures for completing and transmitting AE, SAE, and other reportable safety event reports can be found in Appendix 3.

AE, SAEs, and other reportable safety events will be reported by the participant (or, when appropriate, by a caregiver, surrogate, or the participant's legally authorized representative).

The investigator and any designees are responsible for detecting, documenting, and reporting events that meet the definition of an AE or SAE as well as other reportable safety events. Investigators need to document if an AE and/or SAE was associated with a medication error, misuse, or abuse.

Investigators remain responsible for following up AE, SAEs, and other reportable safety events for outcome according to Section 8.4.3.

The investigator, who is a qualified physician, will assess events that meet the definition of an AE or SAE as well as other reportable safety events with respect to seriousness, intensity/toxicity and causality.

# 8.4.1 Time Period and Frequency for Collecting AE, SAE, and Other Reportable Safety Event Information

All AEs, SAEs, and other reportable safety events that occur after the participant provides documented informed consent but before intervention allocation must be reported by the investigator if the participant is receiving placebo run-in or other run-in treatment, if the event causes the participant to be excluded from the study, or is the result of a protocol-specified intervention, including but not limited to washout or discontinuation of usual therapy, diet, or a procedure.

From the time of intervention allocation through 14 days following cessation of treatment, all AEs, SAEs, and other reportable safety events must be reported by the investigator.

Additionally, any SAE brought to the attention of an investigator at any time outside of the time period specified in the previous paragraph must be reported immediately to the Sponsor if the event is considered related to study intervention.

Investigators are not obligated to actively seek AEs or SAEs or other reportable safety events in former study participants. However, if the investigator learns of any SAE, including a death, at any time after a participant has been discharged from the study, and he/she considers the event to be reasonably related to the study intervention or study participation, the investigator must promptly notify the Sponsor.

All initial and follow-up AEs, SAEs, and other reportable safety events will be recorded and reported to the Sponsor or designee within the time frames as indicated in Table 7.

Table 7	Reporting Time Periods and	I Time Frames for	Adverse Events	and Other
Reportable	e Safety Events			

Type of Event	Reporting Time Period: Consent to Randomization/ Allocation	Reporting Time Period: Randomization/ Allocation through Protocol-specified Follow-up Period	Reporting Time Period: After the Protocol- specified Follow-up Period	Time Frame to Report Event and Follow-up Information to Sponsor:
Nonserious Adverse Event (NSAE)	Report if: - due to protocol- specified intervention - causes exclusion - participant is receiving placebo run-in or other run-in treatment	Report all	Not required	Per data entry guidelines
Serious Adverse Event (SAE)	Report if: - due to protocol- specified intervention - causes exclusion - participant is receiving placebo run-in or other run-in treatment	Report all	Report if: - drug/vaccine related. (Follow ongoing to outcome)	Within 24 hours of learning of event
Pregnancy/Lactation Exposure	Report if: - due to intervention - causes exclusion	Report all	Previously reported – Follow to completion/termination; report outcome	Within 24 hours of learning of event
Event of Clinical Interest (require regulatory reporting)	Report if: - due to intervention - causes exclusion	Report - Potential drug- induced liver injury (DILI) - Require regulatory reporting	Not required	Within 24 hours of learning of event
Event of Clinical Interest (do not require regulatory reporting)	Report if: - due to intervention - causes exclusion	Report - non-DILI ECIs and other events not requiring regulatory reporting	Not required	Within 5 calendar days of learning of event
Cancer	Report if: - due to intervention - causes exclusion	Report all	Not required	Within 5 calendar days of learning of event
Overdose	Report if: - receiving placebo run-in or other run-in medication	Report all	Not required	Within 5 calendar days of learning of event

C Confidential

## 8.4.2 Method of Detecting AEs, SAEs, and Other Reportable Safety Events

Care will be taken not to introduce bias when detecting AEs and/or SAEs and other reportable safety events. Open-ended and nonleading verbal questioning of the participant is the preferred method to inquire about AE occurrence.

## 8.4.3 Follow-up of AE, SAE, and Other Reportable Safety Event Information

After the initial AE/SAE report, the investigator is required to proactively follow each participant at subsequent visits/contacts. All AEs, SAEs, and other reportable safety events, including pregnancy and exposure during breastfeeding, events of clinical interest (ECIs), cancer, and overdose will be followed until resolution, stabilization, until the event is otherwise explained, or the participant is lost to follow-up (as defined in Section 7.3). In addition, the investigator will make every attempt to follow all nonserious AEs that occur in allocated participants for outcome. Further information on follow-up procedures is given in Appendix 3.

## 8.4.4 Regulatory Reporting Requirements for SAE

Prompt notification (within 24 hours) by the investigator to the Sponsor of SAE is essential so that legal obligations and ethical responsibilities towards the safety of participants and the safety of a study intervention under clinical investigation are met.

The Sponsor has a legal responsibility to notify both the local regulatory authority and other regulatory agencies about the safety of a study intervention under clinical investigation. The Sponsor will comply with country-specific regulatory requirements and global laws and regulations relating to safety reporting to regulatory authorities, IRB/IECs, and investigators.

Investigator safety reports must be prepared for suspected unexpected serious adverse reactions (SUSARs) according to local regulatory requirements and Sponsor policy and forwarded to investigators as necessary.

An investigator who receives an investigator safety report describing an SAE or other specific safety information (eg, summary or listing of SAE) from the Sponsor will file it along with the IB and will notify the IRB/IEC, if appropriate according to local requirements.

#### 8.4.5 Pregnancy and Exposure During Breastfeeding

Although pregnancy and infant exposure during breastfeeding are not considered adverse events, any pregnancy or infant exposure during breastfeeding in a participant (spontaneously reported to the investigator or their designee) that occurs during the study are reportable to the Sponsor.

All reported pregnancies must be followed to the completion/termination of the pregnancy. Pregnancy outcomes of spontaneous abortion, missed abortion, benign hydatidiform mole, blighted ovum, fetal death, intrauterine death, miscarriage and stillbirth must be reported as

serious events (Important Medical Events). If the pregnancy continues to term, the outcome (health of infant) must also be reported.

# 8.4.6 Disease-related Events and/or Disease-related Outcomes Not Qualifying as AEs or SAEs

Not applicable.

# 8.4.7 Events of Clinical Interest (ECIs)

Selected nonserious and SAEs are also known as ECIs and must be reported to the Sponsor.

Events of clinical interest for this study include:

1. An elevated AST or ALT lab value that is greater than or equal to 3X the upper limit of normal and an elevated total bilirubin lab value that is greater than or equal to 2X the upper limit of normal and, at the same time, an alkaline phosphatase lab value that is less than 2X the upper limit of normal, as determined by way of protocol-specified laboratory testing or unscheduled laboratory testing.\*

\*Note: This section reflects the handling of nonserious ECI. ECI events meeting SAE criteria are to be reported in the same manner as SAE. The purpose of the criteria is to specify a threshold of abnormal hepatic tests that may require an additional evaluation for an underlying etiology. The study site guidance for assessment and follow-up of these criteria can be found in the Investigator Study File Binder (or equivalent).

# 8.5 Treatment of Overdose

In this study, an overdose is any dose higher than the protocol-specified dose as provided in Section 6.1.

Decisions regarding dose interruptions or modifications will be made by the investigator in consultation with the Sponsor's Clinical Director based on the clinical evaluation of the participant.

### 8.6 Pharmacokinetics

Blood samples for the determination of POS plasma concentrations are to be collected predose, as near the dose as possible, at Day 1 and at the Week 1, 2, 4, 6, 9, and 12 Visits. For participants on the IV formulation, additional samples are to be collected within 15 minutes after the end of infusion at Weeks 1, 2, 4, 6, 9, and 12. The Week 1 postdose PK sample is to be collected after a minimum of 7 days' treatment with POS IV. For participants on oral tablet or PFS formulations who are hospitalized, an additional sample is to be collected between 3 and 6 hours postdose at Weeks 2, 4, 6, 9, and 12. The actual time of blood sample collection should be documented in the participant's eCRF.

If a participant discontinues study treatment early, a plasma sample for drug concentration should be obtained between 8 and 24 hours after the last dose of study treatment. However, if this recommended timing is not feasible, a blood sample should be taken and the date and time of the previous POS dose, as well as the date and time of the blood sample, should be noted in the participant's eCRF.

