### Hypotheses, Objectives, and Endpoints:

There are no hypotheses for this trial. The following objectives and endpoints will be evaluated in male and female pediatric participants aged 2 to <18 years with invasive aspergillosis (IA):

Primary Objectives	Primary Endpoints
- Objective: To evaluate the safety of POS (IV and oral formulations overall)	- Treatment-related AEs
Secondary Objectives	Secondary Endpoints
- Objective: To evaluate the efficacy of POS (IV and oral formulations overall) in participants with possible, probable, or proven IA	- Global clinical response (partial or complete response)
- Objective: To evaluate relapse in participants with possible, probable, or proven IA who have completed treatment with POS (IV and oral formulations overall) and achieved favorable global clinical response (complete or partial)	- Relapse of IA, defined as the re-emergence of clinical, radiographic, or other relevant abnormalities indicating IA
- Objective: To characterize the PK of POS overall and by formulation	- Key PK parameters, consisting of Cavg, Cmin, Cmax, AUC, and Tmax, using sparse plasma concentration sampling (steady state trough and peak)
	- Analysis of exposure-response (efficacy and safety) relationships

- Objective: To summarize the palatability	- Participants' categorical perception of the
and acceptability of POS powder for	taste of the PFS formulation
suspension (PFS) formulation	

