# **1.3** Schedule of Activities (SoA)

Study Period	Screening				Т	reatment						Follow-Up	)	Unsch	Notes
Visit Number/Title	1 Screening	2 Baseline	3	4	5	6	7	8	9	EOTª	10	11	12	Unsch	a. Participants who discontinue study therapy before Wk 12 should have an EOT Visit within 3 days after EOT.
Scheduled Day/ Week and Window	Days -14 to -1	Day 1	Day 3 (±1 day)	Wk 1 (Days 7- 9)	Wk 2 (Days 12-18)	Wk 4 (Days 25-33)	Wk 6 (Days 39-47)	Wk 9 (Days 60-68)	Wk 12 (Days 81-89)	ЕОТ	14 (+2) days after last dose	28 (+2) days after last dose	Day 114 (+7 days)	Unsch b	b. Procedures at unscheduled visits to be performed as clinically appropriate.
Administrative	Procedures														
Assign screening number	Х														
Obtain informed consent/assent	Х														
Issue participant identification card	х	X													See Section 8.1.3
Review inclus./ exclus. criteria	Х	Х													
Medical history	Х														
Prior/concom. medication review	Х	Х	Х	Х	Х	Х	Х	Х	Х	х	Х	Х		х	
Dosing Procedu	ires														
Stratification and treatment allocation no. assigned by IRT		Х													

Study Period	Screening				reatment			Follow-Up		Unsch	Notes				
Visit Number/Title	1 Screening	2 Baseline	3	4	5	6	7	8	9	EOTª	10	11	12	Unsch	a. Participants who discontinue study therapy before Wk 12 should have an EOT Visit within 3 days after EOT.
Scheduled Day/ Week and Window	Days -14 to -1	Day 1	Day 3 (±1 day)	Wk 1 (Days 7- 9)	Wk 2 (Days 12-18)	Wk 4 (Days 25-33)	Wk 6 (Days 39-47)	Wk 9 (Days 60-68)	Wk 12 (Days 81-89)	ЕОТ	14 (+2) days after last dose	28 (+2) days after last dose	Day 114 (+7 days)	Unsch b	b. Procedures at unscheduled visits to be performed as clinically appropriate.
POS (MK-5592) administration		X	X	x	Х	X	х	х	X					х	Daily from Day 1 through Week 12. IV dose on Day 1 BID; subsequent doses QD.
Collect unused medications					Х	Х	Х	Х	Х	Х				Х	For participants
Dosing compliance assessment					Х	х	Х	Х	Х	Х				Х	receiving oral formulations only.
Safety and Tole	erability Pro	cedures													
Vital signs (heart rate, blood pressure, respiratory rate, temperature)	Х	X	X	X	Х	X	X	X	X	X	X	X		Х	While on IV treatment, vital signs to be collected daily. While on oral treatment, vital signs to be collected at each visit.

Study Period	Screening		Treatment										1	Unsch	Notes
Visit Number/Title	1 Screening	2 Baseline	3	4	5	6	7	8	9	EOTª	10	11	12	Unsch	a. Participants who discontinue study therapy before Wk 12 should have an EOT Visit within 3 days after EOT.

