Scheduled Day/ Week and Window	Days -14 to -1	Day 1	Day 3 (±1 day)	Wk 1 (Days 7- 9)	Wk 2 (Days 12-18)	Wk 4 (Days 25-33)	Wk 6 (Days 39-47)	Wk 9 (Days 60-68)	Wk 12 (Days 81-89)	ЕОТ	14 (+2) days after last dose	28 (+2) days after last dose	Day 114 (+7 days)	Unsch b	b. Procedures at unscheduled visits to be performed as clinically appropriate.
Urine or serum pregnancy test (Females of childbearing potential only)	Х	Х				х		Х	Х	х	Х	X			If pregnancy test perform at Screening and Day 1 visit occurs >24 hours later, pregnancy test to be repeated at Day 1 visit.
Full physical examination	Х														
Directed physical examination		Х		Х	Х	Х	Х	Х	Х	х	Х	Х		х	
Body weight (kg)	X	X		X	X	Х	X	X							After Day 1, weight to be measured when oral treatment is initiated (within 3 days before initiating oral treatment).
Height	Х														
AE/SAE Review	Х	Х	Х	Х	Х	Х	Х	Х	Х	Х	Х	Х		Х	

Study Period	Screening				Т	reatment						Follow-Up	)	Unsch	Notes
Visit Number/Title	1 Screening	2 Baseline	3	4	5	6	7	8	9	EOTª	10	11	12	Unsch	a. Participants who discontinue study therapy before Wk 12 should have an EOT Visit within 3 days after EOT.
Scheduled Day/ Week and Window	Days -14 to -1	Day 1	Day 3 (±1 day)	Wk 1 (Days 7- 9)	Wk 2 (Days 12-18)	Wk 4 (Days 25-33)	Wk 6 (Days 39-47)	Wk 9 (Days 60-68)	Wk 12 (Days 81-89)	ЕОТ	14 (+2) days after last dose	28 (+2) days after last dose	Day 114 (+7 days)	Unsch b	b. Procedures at unscheduled visits to be performed as clinically appropriate.
12-lead ECG	х	Х	Х	Х					х	x				Х	Day 1: predose. While on POS IV, ECG to be obtained after completion of infusion. While on oral POS, ECG can be performed without regard to timing of study treatment. See Section 10.7, Appendix 7 for country-specific ECG requirements.
Hematology and serum chemistry	х	X	х	х	Х	х	x	х	х	x	Х	х		х	At Day 1, repeat hematology and chemistry only if >2 days since screening laboratory assessments.

Study Period	Screening		Treatment									Follow-Up		Unsch	Notes
Visit Number/Title	1 Screening	2 Baseline	3	4	5	6	7	8	9	EOTª	10	11	12	Unsch	a. Participants who discontinue study therapy before Wk 12 should have an EOT Visit within 3 days after EOT.

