#### 4 STUDY DESIGN

#### 4.1 Overall Design

This is a nonrandomized, open-label, noncomparative, Phase 2, multi-site trial of POS IV and oral formulations in pediatric participants aged 2 to <18 years with IA, as defined by 2020 European Organization for Research and Treatment of Cancer/Mycoses Study Group (EORTC/MSG) consensus definitions [Donnelly, J. P., et al 2020]. Individuals who meet the criteria for possible, probable, or proven IA will be enrolled.

After a screening period of up to 14 days, participants will be allocated to receive open-label POS study treatment. All participants will initiate treatment with the POS IV formulation. After a minimum of 7 days on POS IV, and when the participant is considered clinically stable and able to take oral study treatment, per investigator judgment, participants may transition to oral study treatment with either the POS tablet formulation or the POS PFS formulation, based on their weight. The initial transition to POS oral formulation (either PFS or tablet) should occur no later than the Week 9 visit and must occur under medical supervision at the study site. After transitioning to one of the oral POS formulations, additional transitions between oral and IV formulations are permitted as clinically indicated.

The planned total duration of study treatment across all formulations is 6 to 12 weeks (42 to 84 days); the actual treatment duration for each participant will be based on the investigator's clinical judgment. Participants should complete all study visits regardless of when they complete study treatment. Doses and additional details of study treatment are provided in Section 6.1.

Safety, efficacy, and PK assessments will be conducted throughout the treatment period, and safety and efficacy assessments at the follow-up visits, 14 (+2) and 28 (+2) days after the last dose of study treatment and at Day 114 (+7 days), as specified in Section 1.3. All participants will be followed for survival through Day 114. The trial's objectives are stated in Section 3 and include safety (primary objective) as well as efficacy, PK, and palatability and acceptability (secondary objectives).

Participants will participate in the trial for up to approximately 128 days: up to 14 days of screening, up to 84 days of treatment, and approximately 30 days of follow-up after the 84-day planned treatment period.

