# 4.3.2 Maximum Dose/Exposure for This Study

For a given participant, the maximum planned dose of POS is 300 mg per administration (administered BID on Day 1 and QD on subsequent days for a maximum of 84 days). Participants who weigh >40 kg will receive the maximum planned dose of 300 mg. The maximum total daily dosing established for this study reflects the approved dose for POS solid oral tablet and POS IV solution formulations, which is 300 mg BID on Day 1 followed by 300 mg QD.

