### 9.1 Statistical Analysis Plan Summary

Key elements of the statistical analysis plan are summarized below; the comprehensive plan is provided in Sections 9.2 through 9.12.

Study Design Overview	A Phase 2, Open-Label, Non-Comparative Clinical Trial to Study the Safety and Efficacy of Posaconazole (POS, MK-5592) in Pediatric Participants Aged 2 to Less Than 18 Years With Invasive Aspergillosis
Treatment Assignment	Pediatric participants aged 2 to <18 years with IA will be allocated to receive POS (Day 1-7 IV formulation, Day 8-84 either IV, PFS or oral formulation). Participants will be enrolled into 2 age cohorts: Age Cohort 1 (2 to <12 years) or Age Cohort 2 (12 to <18 years).
Analysis Populations	Safety: All Participants as Treated (APaT).
	Efficacy:
	
 
Full Analysis Set (FAS) and
 
Responder Population
 

	Pharmacokinetics : All treated participants who receive at least 7 days of POS IV solution and have postdose PK sampling while on POS IV therapy (PK Analysis Population).
	Analysis populations are also defined in Section 9.5.
Primary Endpoint(s)	The primary safety endpoint is the proportion of participants in the APaT population who experience 1 or more treatment-related AEs during POS study treatment (IV or oral) plus 14 days of follow-up.
	There are no primary efficacy or pharmacokinetic endpoints.
Secondary Endpoints	• Proportion of participants in the FAS population with a favorable global clinical response (partial or complete response) at the Week 6 (Day 42) Visit, at the Week 12 (Day 84) Visit, and at the EOT Visit (if different).
	• Proportion of participants in the Responder Population who have a relapse of IA at any point after achieving favorable global clinical response through 28 days post-treatment.
	• Cmin, Cmax, and Tmax, based upon sparse PK sampling (peak and trough concentration).
	• Analysis of exposure-response (efficacy and safety) relationships.
	
 
Participants' categorical perception of palatability and acceptability of the PFS formulation.
 

Statistical Methods for Efficacy/Immunogenicity/ Pharmacokinetic Analyses	Efficacy endpoints- overall proportion of participants in the FAS population with a favorable global clinical response at the Week 6, the Week 12, and the EOT Visits – will be estimated and the corresponding 95% confidence interval (CI) provided using the Clopper-Pearson method.

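### The Week 12 visit window (Days 81-89) runs past the 84-day dosing maximum, so a participant who completes on Day 84 can have no Week 12 postdose sample, a washout value for a trough, and an off-treatment ECG

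*Combined protocol and SAP*

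**What the plan says.** **Visit window and dosing note.** The Schedule of Activities (Section 1.3) heads the column "Wk 12 (Days 81-89" and marks drug administration, plasma PK, 12-lead ECG and hematology/chemistry at that visit. Its dosing note reads "Daily from Day 1 through Week 12" and gives no day number. The summary in Section 9.1 places response assessment "at the Week 12 (Day 84) Visit".

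**Dosing limit.** Section 4.3.2 has drug "administered BID on Day 1 and QD on subsequent days for a maximum of 84 days". Section 4.1 describes "up to 14 days of screening, up to 84 days of treatment". The synopsis and Table 3 give the oral regimen as Days 8 to 84.

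**Samples and ECG tied to a dose.** Section 8.6 requires a predose sample at Week 12. For participants on IV, "additional samples are to be collected within 15 minutes after the end of infusion at Weeks 1, 2, 4, 6, 9, and 12". Hospitalized participants on an oral formulation have a sample 3 to 6 h after the dose. The ECG note says "While on POS IV, ECG to be obtained after completion of infusion"; on oral drug the ECG may be done at any time relative to dosing.

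**Rules anchored to the last dose.** Section 8.6 sets a sample 8 to 24 h after the last dose, but only for early discontinuation. Section 8.9.2.3 sets an EOT visit within 3 days, but only for those who stop before 12 weeks.

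**Use of the data.** The PK endpoint is obtained "using sparse plasma concentration sampling (steady state trough and peak". Section 9.4.1.2 takes observed peak and trough directly from these samples. Section 9.6.3 summarizes ECG and laboratory change from baseline at the scheduled time points. Neither section has a rule on time since the last dose.

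**The concern.** The window is centred on the day after the last permitted dose. For a visit on Days 85-89 a site can follow the Schedule of Activities and dose at the visit, which exceeds the 84-day maximum. Or it can keep to the maximum and carry out dose-anchored procedures with no dose to anchor them. A participant who completes on Day 84 falls under neither of the rules written for stopping.

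At stake are the last on-treatment PK time point and the last scheduled on-treatment ECG and laboratory values. A low concentration recorded as a Week 12 trough would pull observed late-treatment exposure downward. ECG and laboratory values reported as Week 12 on-treatment changes would include some taken off drug. About 30 participants are planned, and only those treated to about Day 84 contribute, so a few such values could show in a descriptive summary.

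**Working it through.** **1. The plan's own timeline.** Section 4.1: 14 days of screening + 84 of treatment + about 30 of follow-up = 128 days, as stated; 84 + 30 = Day 114, the mortality visit. The timeline therefore rests on treatment ending at Day 84.

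**2. Planned samples.** Table 12 allots 0.35 mL for PK on Day 1, where only a predose sample is due, and 0.7 mL at Week 12. The row total reproduces: 0.35 + 6 × 0.7 + 0.35 + 0.7 = 5.6 mL. So the Week 12 volume provides for two samples.

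**3. Counting the window.** Length: 89 − 81 + 1 = 9 days. Midpoint: (81 + 89)/2 = Day 85.

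- Days after a Day 84 last dose: 85-89, so 5/9 = 55.6%.
- Days more than 24 h after that dose at the same clock time: 86-89, so 4/9 = 44.4%.
- No other treatment-visit window reaches Day 84; Week 9 ends on Day 68.

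**4. What a Day 84 completer can provide.**

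| Visit day | Trough | Postdose sample | ECG and laboratory values |
|---|---|---|---|
| 81-84 | Yes | Yes | On a dosing day |
| 85 | Yes, about 24 h after the dose | Not obtainable | After last dose, within about 24 h |
| 86-89 | Washout value | Not obtainable | After last dose, beyond 24 h |

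**5. How low a washout value might read.** The documents give no half-life, so this step rests on an assumed range of 12 to 48 h and simple exponential decay. Fraction of the true 24 h trough = 0.5^((t − 24)/half-life), with t the hours since the Day 84 dose.

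| Visit day | t (h) | 12 h | 24 h | 36 h | 48 h |
|---|---|---|---|---|---|
| 86 | 48 | 25% | 50% | 63% | 71% |
| 87 | 72 | 6% | 25% | 40% | 50% |
| 89 | 120 | 0.4% | 6% | 16% | 25% |

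**6. Where a post-treatment flag could start.** Section 8.1.8 lets a delayed dose be given until 6 h after it was due. A compliant predose sample can therefore be 24 + 6 = 30 h after the previous dose. A limit built from the ±3 h adjustment alone (24 + 3 = 27 h) would discard some valid troughs.

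**The case against.** The plan evidently intends Week 12 to be a dosing-day visit: the Schedule of Activities marks administration there, and Section 8.6 wants the predose sample close to the dose. Cmax, Cmin, Cavg, AUC and Tmax are to come from a population model using actual doses (Section 9.6.2), with sample times (Section 8.6) and dose times (Section 9.11) recorded, so late samples can be handled correctly. Section 9.6.2 sets out no by-visit table of observed troughs, and the separate Modeling Analysis Plan is not available here. Few participants should be on IV at Week 12, since the first switch to oral is due by the Week 9 visit. The oral postdose sample is for hospitalized participants only. A Day 85 ECG in an oral participant is no further from the dose than an ECG the plan already allows.

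All of this stands and limits the size of the problem. It does not remove the conflict, because dosing at a visit on Days 85-89 is exactly what the 84-day maximum rules out.

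Three stronger readings are tempting but unsupported:

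- *A washout value could be reported as a Week 12 peak.* The peak sample is defined by a dose shortly before it. With no dose it is missing, not mislabelled.
- *Over half the window gives invalid troughs.* Day 85 is still a 24 h trough, so the count is 4 of 9, not 5 of 9.
- *Week 6 has the same fault for a child who stops on Day 42.* That child has an EOT visit within 3 days, by about Day 45. It replaces Week 6 because it falls inside Days 39-47, and Table 12 allots it a single 0.35 mL PK sample.

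**Conclusion.** The concern holds in limited form. The Week 12 window and the dosing note do not agree with the 84-day maximum and the Days 8-84 oral regimen, and the plan has no rule for a Day 84 completer seen afterwards. The postdose sample is unobtainable on 5 of 9 allowed days, and a trough would be a washout value on 4 of 9. ECG and laboratory values on the same 5 days follow the last dose.

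The counts assume uninterrupted dosing with the last dose on Day 84. They describe the window, not the share of participants affected, because the documents give no distribution of visit days. The residual percentages depend on the assumed half-lives. The size of any effect on ECG or laboratory summaries cannot be derived from the documents.

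A reader might infer that the PK parameters or the primary endpoint are compromised. The documents do not support that: the parameters are model-derived from recorded times, and treatment-related AEs are counted through 14 days after treatment. This is a low-cost improvement to data at one visit.

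**What to change.** 1. Reconcile the dosing note and the Week 12 window in the Schedule of Activities with the 84-day maximum in Section 4.3.2 and the Days 8-84 regimen in Table 3. Which of these is right is for the sponsor to decide.
2. Keep the visit window, but add a note to the Schedule of Activities that the Week 12 PK samples and ECG are taken on a day of dosing or, failing that, that a single PK sample is taken about 24 h after the last dose.
3. State in Section 9.4.1.2 that Week 12 samples taken after the final dose, and later than the next dose could have been given (about 30 h), are flagged as post-treatment. They would be used in the population model at their actual times and left out of observed steady-state trough summaries.
4. State in Section 9.6.3 that Week 12 ECG and laboratory values obtained post-treatment are flagged likewise.

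The cost is one schedule note, a sentence in each of two SAP sections, and a few days less scheduling freedom for PK and ECG at one visit.
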